2. RATIONALE						
3. THEORETICAL FRAMEWORK						
4. RESEARCH QUESTION/AIM(S)						
5. STUDY DESIGN/METHODS						
6. STUDY SETTING						
7. SAMPLE AND RECRUITMENT						
8. ETHICAL AND REGULATORY COMPLIANCE						
9. DISSEMINATION POLICY						
10. REFERENCES						
11. APPENDICES						

KEY STUDY CONTACTS

Chief Investigator	[name]				
	[contact]				
	[contact]				
Study Co-ordinator	CI above will cover these duties				
Sponsor	University Hospital Southampton NHS Foundation Trust [name]				
	University Hospital Southampton NHS Foundation Trust				
	[name]				
	Southampton				
	[name]				
	[contact]				
	[contact]				
Joint-sponsor(s)/co-sponsor(s)	n/a				
Funder(s)	NIHR				
Key Protocol Contributors	[name]: [contact]				
	[name]: [contact]				
Committees	The PPI Advisory Group is established. The Study Steering Committee will be in place by end of February 2025				

STUDY SUMMARY

Study Title	Improving the care people with learning disabilities receive in hospital: an ethnographic study examining the experiences of people with learning disabilities and the organisation and delivery of their care
Internal ref. no. (or short title)	Care4Me
Study Design	This project will use ethnography (with 8 case study adults with learning disabilities and carers (estimated n=16-24) and staff (estimated n=64) involved in their care, using observation, interviews, document analysis) to understand how care is experienced by adults with learning disabilities and how it is organised and delivered by ward teams during a hospital admission.
Study Participants	Adults with learning disabilities who are admitted within two large general hospitals in England over a four-month period. We will include a range of participants who have had particular types of experiences (critical case sampling) to

	ensure we include people with learning disabilities who are typically excluded from research. Sampling will include adults with a learning disability who represent a range of factors that may influence care delivery, and where possible, sociodemographic factors: - Severity of learning disability (mild to profound) - Primary reason for the admission, including planned and unplanned admissions People from Black, Asian, and Minority Ethnic groups with a learning disability Expected length of stay - To include people attending hospital with differing levels of support, who have a full-time family or professional carer, and who have limited or no support.				

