People with learning disabilities have also been under-represented in research about their care. Methods that exclude people with severe or profound learning disabilities (10–15) are common and can be poorly implemented with people with mild learning disabilities (16–18).

Brief description of the study

In response, this exploratory study will provide a detailed examination of the experiences of adults with learning disabilities and the organisation and delivery of their care during a hospital admission. Objectives are to:

- 1. Understand care experiences from the perspectives of adults with learning disabilities and family carers during a hospital admission, including people with complex needs and profound learning disabilities.
- 2. Examine how care is organised and delivered for adults with learning disabilities during a hospital admission including how ward teams understand and respond to their needs.
- 3. Use the findings to co-design guidance with people with learning disabilities, carers and ward staff to deliver initial strategies to improve support for people with learning disabilities at the ward level during hospital admissions.

Methods

We will carry out ethnographic research following 8 case studies of adults with learning disabilities and their carers and hospital staff supporting and caring for them across a hospital admission, which will provide the detailed understanding of how care is organised, adapted and delivered at ward level, including how reasonable adjustments are made. We will include people from minority ethnic groups and people with profound learning disabilities in our sample, broadening our understanding of the hospital experience for both groups and developing new methodological approaches to the inclusion of people with profound learning disabilities in hospital research.

We will carry out the research in two hospitals using ethnographic methods: observation, interviews and document analysis. We will use a toolbox of accessible interview supports and spend time with people with profound and multiple learning disabilities during a hospital admission to learn about, include and interpret their non-verbal communications with the support of their carers.

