This project will use ethnography (with embedded case studies, observation, interviews, document analysis) to understand how care is experienced by adults with learning disabilities and how it is organised and delivered by ward teams during a hospital admission. JH will carry out all data collection and analysis with the support and mentoring of KF. As described below, PPI groups will also be involved in the analysis and interpretation of data.

In response to objective 1 we will recruit 8 case studies of adults with learning disabilities (4 per hospital) who are admitted within two large general hospitals in England over a four-month period and their carers and hospital staff supporting and caring for them.

For each case study, ethnographic in situ interviews with adults with learning disabilities and family carers will be carried out to explore their experiences of care during their hospital admission. We estimate carrying out a series of at least four ethnographic interviews with each person with a learning disability and/or their family carers during their admission (total n=>32 interviews) as well as spending time 'alongside' adults with profound and multiple learning disabilities observing and interpreting their non-verbal communication with the support of their carer(s).

Drawing on team expertise (JH) in supporting, interviewing, and observing the care of adults with learning disabilities (including adults with profound learning disabilities), and involving vulnerable populations in research during a hospital admission (KF), we will use tailored methods of augmentative and adaptive communication for each participant and accessible interview tools. These will be agreed in discussion with the person and (if appropriate) their carer. For adults who communicate nonverbally or with few words, JH will work with their carer to interpret how they express assent, dissent and a range of emotions.

For all participants including those with varying degrees of verbal communication we will build on existing good practice in the use of interviews with people with learning disabilities (22,42,54,59). Our toolbox of adapted and augmentative supports will include adaptations that have already been successfully used on hospital studies with people with learning disabilities:

- Talking Mats (www.talkingmats.com), "a facilitated conversation approach used to supplement interviews by moving graphic images around to make options more concrete" (22,54,59)

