- Use of pictures to guide discussion (59)
- Pictures and stories about care experiences (following (40))
- Use of a sticker activity about interactions with staff using happy and sad faces (59)
- Use of symbols including Makaton to support questions about care (following (22))

For people with profound learning disabilities these methods will not be appropriate, however, with support people may be able to express preferences or emotional responses to the here and now (54) Building on the most innovative work to date with people with profound and multiple learning disabilities, JH will spend significant periods of time 'being with' (62) each individual during their hospital admission to understand the meaning of each participant's "personalised forms of action" and through negotiating and interpreting meaning with their carer (60) We will be guided by their carer(s)' advice on how best to spend time with and interact with the person (61) and how they express a range of emotions (fear, pain, boredom, frustration, contentment) (60). This will involve recording detailed 'micro-descriptions' of their body and facial movements, with interpretations discussed with their carer(s) during the admission (60,61,64)

This will produce detailed understandings of care experiences from the perspectives of adults with learning disabilities and family carers during a hospital admission, including people with complex needs and profound learning disabilities.

In response to objective 2,

At ward level, for each case study participant, we will observe (where possible) the routine bedside care they receive during their admission. Ethnographic observations will focus on:

- routine care at the bedside including: mealtimes and hydration; personal care (we will not observe intimate care); observations and medication rounds (including vital signs); to provide understandings of the routine organisation and delivery of care.
- staff attending the bedside and visits from specialists (including Learning Disability Liaison Nurses, medical teams, Speech and Language Therapists, and Physiotherapists) to examine interactional approaches during everyday care.
- nursing handovers, medical rounds, and MDTs (as they relate to the case studies) to examine decision making, involvement of the person and family, any adaptions, and discharge plans.

In addition:

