-Ethnographic in situ short interviews with ward staff attending the bedside (approximately 8 per case study) and directly caring for participants to explore how they understand the participant's care and communication needs.

- -Documentary examination of hospital passport and medical records to examine care across the admission and how it is recorded.
- -Ward level documentation on staffing levels and patient acuity during the periods of observation to provide context.

The four-month period of data collection will deliver 160 hours of detailed ethnographic observations, across the two hospital sites. Observation periods will be carried out over three days/shifts a week across their admission, providing approximately 20 hours per case study. Observational fieldnotes and in situ short interviews will be taken during observation periods and written up into more detailed data on the same day (producing approximately 175,000 words of data). No identifiable data (individual names, ward names, hospital name) will be recorded during data collection. All notes will use pseudonyms for patients and carers, and staff role only will be used in notes.

This will produce new understandings of how care is organised, adapted, and delivered for adults with learning disabilities during a hospital admission including how ward teams understand and respond to their needs.

Analysis

Data sets will be transcribed by JH into anonymised word documents or collected using handwriting software on a tablet and converted into Word files. Data will be checked and cleaned in Word. All tablets are provided by University of Southampton and password protected. These word documents will be entered into NVivo for analysis. The goal of analysis will be to create a conceptual model of how care is organised, adapted, and delivered for people with learning disabilities during a hospital admission via: (1) a narrative approach to deliver a series (n=8) of detailed case studies (interviews, observation, document analysis) that illuminate individual trajectories during an admission. This will illustrate the experiences of a range of people with learning disabilities across different clinical contexts, experiences, and outcomes. These case studies will be used to inform theory development to support and extend the ethnographic analysis of everyday care. They will also be used to inform output development including anonymised case scenarios.

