- (2) To analyse the ethnographic data (observation, in situ interviews, document analysis) an inductive process will be used, drawing on a grounded theory approach. To develop concepts and theories from the data we will develop initial 'sensitising concepts', using the constant comparative approach to deliver understandings about the provision of hospital care for people with learning disabilities that are transferable beyond local contexts (100)
- (3) The ethnographic and case study analyses will be examined, refined, and brought together during the process of co-production to develop strategies to support hospital care. We will use NVivo to manage data and analysis, enabling us to develop a wider conceptual analysis and detailed case studies that illuminate key concepts and theory development.

We will also use this study to provide an analysis of the practicality and acceptability of the research methods used (inclusive interview and observational approaches). Ethnography is appropriate to support this through detailed recording in-situ of the methodological approach in practice.

Participant details will remain confidential as per the requirements of the Data Protection Act (2018) and the University Hospital Southampton NHS Foundation Trust data management policy. Linked anonymity will be guaranteed (each participant will be allocated an ID on entry to the study and code and participant list will be stored separately). The code sheet that links codes with individual identifying

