Patients can participate in the research without giving consent for their medical notes to be accessed by the researcher and/or for the researcher to make notes during staff meetings about their care. This will be made clear in discussion and is clear on the information and consent sheets. If consent is given for accessing medical records, or a consultee advises that they can be accessed, brief notes will be taken to outline the treatments and assessments undertaken. These will be used to support the interviews with patients, who may, due to their learning disability, find it difficult to remember the details of their hospital treatment and assessment

At the beginning of each planned data collection session the researcher will check if the person and (if relevant) their carer(s) are happy for her to continue, including a discussion about whether the person feels too unwell to participate in observations or interviews that day or too unwell to continue participating in the study. This will be done in a way appropriate to that person's ability to communicate and understand. If anyone shows signs of not wanting the researcher to carry out the study with them at that time, she will stop collecting data that day. If this happens again the next day, the researcher will withdraw that person from the study completely. If a patient or carer says at any point they don't want to be in the study anymore, or it is their view (or the view of their personal consultee) that the patient does not wish to participate any longer the researcher will withdraw that person from the study completely.

It is possible that existing participants may move onto an End-of-life care pathway or into an Intensive Care Unit. If this happens, we will review their participation with them with the support of their carer or personal consultee if relevant and withdraw them from the study at this point if they wish.

If a participant with a learning disability wishes to withdraw their data from the study, they can do so during the data collection period, but not afterwards. This is made clear on the information sheets and will be discussed with all potential participants.

Carers

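### Do sections 5 and 7.3.2 of the protocol conflict on what the medical-record notes are for?

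*Protocol*

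**What the plan says.** Section 5 (Study Design and Methods), under objective 2, lists the data to be gathered on the organisation and delivery of care. One item is "Documentary examination of hospital passport and medical records to examine care across the admission and how it is recorded". A separate item covers ward-level documents on staffing and patient acuity. Under Analysis, the same section makes documents one component of "detailed case studies (interviews, observation, document analysis) that illuminate individual trajectories during an admission". It also counts them among the material analysed inductively: "To analyse the ethnographic data (observation, in situ interviews, document analysis) an inductive process will be used". The study summary and section 1 name document analysis as a method in general terms ("using ethnographic methods: observation, interviews and document analysis").

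Section 7.3.2 (Consent, people with learning disabilities) says that the researcher will ask the patient for verbal and written consent to access the medical records and take brief notes from them. If the patient lacks capacity, a consultee is asked for advice. The patient may refuse this access and still take part. Where access is agreed, "brief notes will be taken to outline the treatments and assessments undertaken. These will be used to support the interviews with patients", the reason given being that patients may find it hard to recall the details of their treatment. The hospital passport is named in section 5 and not in 7.3.2.

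**The concern.** The two sections appear to give different instructions for one activity, and they differ in three ways. On source, section 5 names the passport as well as the records, while 7.3.2 names only the records. On content, section 5 wants evidence of care across the admission and of how it is recorded, while 7.3.2 describes an outline of treatments and assessments. On use, section 5 says analysis, while 7.3.2 says interview support.

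If the consent section set the limit, the notes could be too thin to show how care is recorded. If section 5 set it, the researcher would be noting more than the consent section describes, from confidential records of people some of whom lack capacity. Record access is a separate and optional decision, so its described purpose ought to match the planned use. The interview-support purpose also sits awkwardly with participants who have profound learning disabilities, since section 5 says the interview tools will not suit them.

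**Working it through.** No arithmetic applies: neither passage gives a figure, and no estimate or sample size depends on them. The check is to read the passages against each other.

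1. **Does 7.3.2 restrict the use of the notes?** The sentence on what consent is sought for covers access and brief notes, with no limit on use. The later sentence ("brief notes will be taken to outline the treatments and assessments undertaken. These will be used to support the interviews with patients") names a use and explains why it helps. It does not say that this is the only use.

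2. **Does anything withdraw the analytic use in section 5?** No. The Analysis text keeps documents as an input to both the case studies and the inductive work ("To analyse the ethnographic data (observation, in situ interviews, document analysis) an inductive process will be used"). Section 5 sets out data sources and analysis, and 7.3.2 sets out how permission is obtained. Each can stand while doing its own job.

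3. **Can one set of notes serve both purposes?** Largely. Treatments and assessments taken from the record are part of care across the admission, and what the record contains shows at least in part how care was documented. A bare outline would be thin evidence on recording practice, but section 5 tells the researcher that recording is of interest.

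4. **Does the silence on staff meetings help in reading the text?** Somewhat. Section 7.3.2 asks permission to take notes in staff meetings and gives no use for them. Section 5 supplies it: "to examine decision making, involvement of the person and family, any adaptions, and discharge plans". So the consent section is not a full statement of research purposes. The parallel is partial, because for records 7.3.2 does state a use.

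5. **How widespread is the mismatch?** It is one item in section 5 against one description in 7.3.2. The general mentions of document analysis elsewhere do not enlarge it, because that term also covers the ward staffing and acuity documents, which patient-record consent does not concern.

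6. **Is the passport outside the consent?** This cannot be settled from the protocol. Section 5 lists the passport beside the medical records, and nothing says whether it is held as part of them. The information and consent sheets, which would settle what participants and consultees are told, are not available.

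7. **What of participants with profound learning disabilities?** The tools described as unsuitable are communication aids for interviews. Section 5 allows interviews with the person, the family carers or both. Where no patient interview takes place, nothing in 7.3.2 prevents the notes from being used as section 5 plans.

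8. **Who acts on the two descriptions?** Section 5 assigns all data collection and analysis to one researcher, the chief investigator, with mentoring. Different staff following different descriptions is therefore not a practical risk.

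**The case for a change.** The strongest case for a change is that 7.3.2 does not merely stay silent. It states a content and a purpose, and both are narrower than those in section 5. A dual purpose could have been written down and was not. The data-protection text in section 8.6 does not join the two descriptions. An ethics committee or monitor reading only the consent section would take the notes to be an interview aid, and section 5 lists the passport as a separate source.

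The difference in wording stands, and so does the omission of the passport from 7.3.2. The step from there to an operational conflict does not. It would require reading the stated use as exclusive, which the text does not say. Section 8.6 adds little either way: its sentence on collecting only necessary information goes on to names and contact details, so silence there about record notes is unsurprising.

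The obvious remedy, widening 7.3.2, is also not clearly an improvement. It would enlarge the described note-taking from confidential records of people who may lack capacity, and it might need an amendment if the participant materials are narrower. Narrowing section 5 would reconcile the text equally well. Which way to go is for the investigators and the ethics committee, and the protocol alone gives no ground for preferring either.

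**Conclusion.** No change to the plan follows. The two sections describe record use at different breadth, and 7.3.2 leaves out the hospital passport, but they can be read together: the notes help patients who are interviewed and also enter the document analysis planned in section 5. A researcher who designed the study and does all the data collection can fill this gap sensibly.

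The effect on results is not computable and there is no sign that it is material. At most one strand of objective 2, how care is recorded, could be thinner if the notes were kept to a bare outline. The observations and staff interviews that carry most of that objective are untouched.

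The conclusion rests on two assumptions: that the stated interview use is not meant to be exclusive, and that the unseen information and consent sheets describe record access in terms compatible with section 5. If the sheets proved narrower, that would be a separate matter of consent. A cross-reference between the sections at a future revision would be tidy, but it would mainly write into 7.3.2 what section 5 already says.

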If the participant with a learning disability says they are happy for their carer(s) to be included, the researcher will provide the carer(s) with information and consent forms and discuss the study with them too. The carer will be required to give written consent to participate. If the carer does not wish to take part but the patient does, the researcher won't collect any data about them, including during observations of the patient's care if they are present.

Staff

The study focus is on observing the everyday care provided to people with learning disabilities by nursing and HCA staff (and other clinical staff from a range of disciplines and roles when they are involved in the care of our participants with learning disabilities). We have built on the approaches

used in previous NIHR grants using observations, approved by the HRA (NIHR13290; NIHR170503) and agreed this process with guidance from our NHS collaborators.

When consent has been gained for a patient to participate in the study, written consent will be sought from the ward manager or nurse in charge for the researcher to be present on the ward and observe care. The researcher will put up posters about the research in prominent places and leave information sheets at the nurse's station. The researcher will request that the relevant member of staff add a research entry to the patient's medical notes documenting their consent process according to local standard research policy.

The researcher will sit near the patient participant during her observations, explain the study and seek verbal consent from staff. Staff members can cease participation at any point during the study.

Nursing staff will be approached at a time that does not interrupt care to ask for full written consent to participate. Should a staff member decline to give written consent, any data collected about or from them during that observation period will be destroyed and they will not be observed in any subsequent care observations. However as notes on care provided by staff are anonymous, it will not be possible to remove data about prior observations on different shifts.

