Written consent from the ward manager will be sought for attending meeting discussions about the patient's care. The researcher will ask for verbal consent from all staff in the meeting and if all staff do not agree, she will not take notes of their contribution. It is not practical to take consent from staff from other parts of the hospital as this may entail interrupting ward processes or interventions. Instead, posters giving information about observations on the ward will be prominently placed at the entrance to the room where observation of the patient is taking place. As described above, a note will be added to the patient's medical record to identify them as a participant in research, according to local standard research procedures. The researcher will carry information sheets and be available to answer questions and will take verbal consent from all staff when it does not interfere with clinical care processes or the work of the ward. An observation will be ceased should any staff member raise any concerns about being observed.

If the patient participant moves to another ward during data collection (including into an Intensive Care Unit or after moving onto an End-of-life care pathway), the researcher will explain the study to the new ward manager and seek initial verbal consent to continue the study on that ward if the patient participant (or on advice from a consultee) wishes to continue. She will check that the patient and their carers (if relevant) are happy to continue with the study on this new ward. She will then use the same recruitment and consent process for the ward manager and staff as described above, for this new ward.

RIGHT TO WITHDRAW

The participant will remain free to withdraw at any time from the study without giving reasons and without prejudicing his/her further treatment and will be provided with a contact point where he/she may obtain further information about the study. Participant withdrawal of consent from the study will be explicitly documented in the source documents.

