Linked anonymity will be guaranteed (each participant will be allocated an ID on entry to the study and code and participant list will be stored separately). The code sheet that links codes with individual identifying details will be stored on a password protected file on a password protected computer, and in a locked filing cabinet, separate to any research data storage. Any research data stored will be associated with individual codes not identifying details. All physical data will be stored in a locked cabinet at the University (paperwork) all electronic data on a password protected file on a network drive that is accessible only through the research team members' password protected accounts. This will only be accessed by members of the research team. Files relating to the project may sometimes be stored on researchers' local laptop disks, which are protected by a university login. However all sensitive files will be stored on the network drive where feasible, or if away from network access and access is critical, saved to the local laptop disk with a password known only to the research team. Data will be archived for 15 years in accordance with the University Hospital Southampton NHS Foundation Trust's Research Data Management Policy, and the CI will retain anonymised data from the study for use in further publications.

All information sheets and consent forms state that participants in the research are guaranteed anonymity. All contact details will be stored securely and destroyed after the final key output or summary document from the study is shared with prior participants. This data will play no part in any dissemination or outputs of the study and will be managed in line with UK General Data Protection Regulation

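### Does keeping earlier-shift notes on a nurse who declines written consent break the protocol's promise of a linked ID for every participant?

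*Protocol*

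**What the plan says.** Three parts of the protocol bear on this.

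- **How staff appear in the data.** Section 5 states: "All notes will use pseudonyms for patients and carers, and staff role only will be used in notes". Section 8.6 repeats this and adds ward speciality.
- **What is promised on identifiers.** The analysis part of section 5, and again section 8.6, state: "Linked anonymity will be guaranteed (each participant will be allocated an ID on entry to the study", with the list held separately. Section 8.6 adds: "Any research data stored will be associated with individual codes not identifying details". Neither place limits these statements to patients and carers.
- **How staff consent works (section 7.3.2).** Verbal consent is sought from staff during observation. Then: "Nursing staff will be approached at a time that does not interrupt care to ask for full written consent to participate". If a staff member declines, data about or from them in that observation period are destroyed and "they will not be observed in any subsequent care observations". The retention rule follows: "However as notes on care provided by staff are anonymous, it will not be possible to remove data about prior observations on different shifts".

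Section 7.3.2 handles other refusals differently. "If the carer does not wish to take part but the patient does", nothing is collected about the carer. Where staff in a meeting do not agree, "she will not take notes of their contribution".

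**The concern.** Read side by side, the passages seem unable to hold together. Staff are counted in the sample, so they look like participants with an ID and coded data, yet their notes carry no code and are said to be untraceable. The gap also looks avoidable. Written consent has no latest point, so it may first be asked on a later shift, and the researcher must in any case recognise a decliner in order not to observe that person again. Carers and meeting attendees appear to be better protected.

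At stake would be which staff notes stay in the material feeding the eight case narratives and the constant-comparative analysis, and what staff can truthfully be told about tracing and removing their data.

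**Working it through.** **Inputs.** Eight cases, 16 to 24 carers, 64 staff, total 96 (section 7.2.1). About 8 staff interviews per case, three observed days or shifts a week, about 20 hours per case and 160 hours overall (section 5). Stays of 3.7 days on average, up to 7.4 days in some departments (section 7.2.1).

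**1. The plan's own figures.**
- Staff: 8 × 8 = 64, as stated.
- Total: 8 + 24 + 64 = 96, as stated, using the upper carer figure. With 16 carers it is 8 + 16 + 64 = 88.
- Staff share: 64/96 = 66.7% or 64/88 = 72.7%. Staff are clearly part of the stated sample.
- Hours per case: 160/8 = 20, as stated.

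**2. How many earlier shifts could be affected.**
- Observed shifts per case = 3/7 × length of stay: 3/7 × 3.7 = 1.6, and 3/7 × 7.4 = 3.2.
- Shifts before the last observed one: 1.6 − 1 = 0.6, and 3.2 − 1 = 2.2.

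This assumes observation runs from the first day of the stay. It starts only after recruitment, so for a given stay the true number is lower. Stays longer than 7.4 days would raise it.

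**3. What must happen for notes to be kept after a refusal.** All of these are needed:
- the same nurse is at the bedside on two observed shifts of one case;
- the nurse is recorded on the earlier shift;
- written consent is not asked for on that shift;
- it is asked for later;
- the nurse then refuses.

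The protocol gives no probability for any step, so the joint frequency cannot be calculated. Its lower bound is zero.

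**4. Is the identifier wording a real contradiction?**
- *Decliners.* IDs are given on entry to the study. A nurse who declines written consent can be read as never having entered, so the ID promise need not reach that person.
- *Consenting staff.* Section 8.6 says names are taken for consent forms, so a list of staff IDs can exist alongside notes that show role only. The two are compatible.
- *Stored data.* The sentence that any stored data carry individual codes is not literally met by role-only staff notes. Its evident purpose is to keep identifying details out of the stored data, and role-only notes meet that purpose. What remains is a sentence drafted for patients and carers and worded too widely.

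**5. Would closing the gap improve anything the study estimates or concludes?** The analysis (section 5) builds case narratives around patients and concepts about how care is organised. No planned analysis follows an individual staff member across shifts. Neither tighter wording nor an earlier consent request alters a sample size, a precision or a conclusion.

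**The case for a change.** The strongest case against leaving this alone is that the text does say *any* stored research data, staff who consent are still recorded by role only, and if a decliner never entered the study, the kept notes describe a non-participant. With up to about two earlier shifts in a case, a late consent request is realistic. Asking within the first observation period would bring a refusal under the existing destruction rule and cost little.

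The literal mismatch in sections 5 and 8.6 stands. The rest carries less weight:

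- The retention rule is disclosed and reasoned. The protocol says its approach to staff builds on earlier approved observation studies and was agreed with the NHS collaborators.
- The kept notes are not simply unconsented. Verbal consent is sought, the ward manager consents in writing, posters and information sheets are displayed, and an observation stops if any staff member raises a concern.
- The destruction rule already speaks of the observation period in which the refusal occurs, so asking within the period is foreseen. A fixed deadline would compete with the commitment not to interrupt care.
- Recognising a person so as not to observe them again is different from finding that person afterwards in notes that show only a role. To allow tracing, one nurse's entries would have to be linked across shifts. That weakens staff anonymity in a study that expects it may see unacceptable practice (section 8.1).
- Carers are not a like-for-like comparison, because they give written consent to take part. Limits on removal are not unique to staff either: patients cannot withdraw data once data collection has ended.
- The staff information sheet is not among the material available, so it cannot be said to mislead.

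**Conclusion.** No change to the plan follows. The linked-ID and coding statements are worded more widely than the handling of staff notes. This is a drafting slip that a reader resolves from the explicit role-only rule in sections 5 and 8.6 and the explicit retention rule in section 7.3.2. Keeping earlier-shift notes is a fair trade-off: it gives up removal in a narrow set of circumstances in return for notes that do not single out individual staff.

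The reach is small. It covers at most the notes from about 0.6 to 2.2 earlier shifts per case, only for time when the decliner was at the bedside, and only if every step of the chain occurs. These figures rest on the protocol's stays of 3.7 to 7.4 days and three shifts a week. The number of staff affected cannot be estimated from the protocol and may be zero. The conclusion also rests on the individual staff member not being a unit of analysis, which is how section 5 reads. If the analysis came to depend on tracing individual staff across shifts, the point would need to be looked at again.
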